5.3 Screen Failures

Screen failures are defined as participants who consent to participate in the clinical trial but are not subsequently randomly assigned to the study intervention or entered in the study. A minimal set of screen failure information is required to ensure transparent reporting of screen failure participants, to meet the Consolidated Standards of Reporting Trials (CONSORT) publishing requirements and to respond to queries from regulatory authorities. Minimal information includes demography, screen failure details, eligibility criteria, and any serious adverse event (SAE).

Individuals who do not meet the criteria for participation in this trial (screen failure) may be rescreened once at the Investigator's discretion.

6 STUDY INTERVENTION

6.1 Investigational Products dMAb AZD5396 and dMAb AZD8076

dMAb AZD5396 contains plasmids pGX93321 and pGX93311 that encodes for the heavy and the light Ig chains of optimized mAb AZD5396; dMAb AZD8076 contains plasmids pGX93322 and pGX93315 that encodes the heavy and the light Ig chains of optimized mAb AZD8076 monoclonal antibody against SARS-CoV-2 virus.

6.1.1 Acquisition and Accountability of dMAb AZD5396 and dMAb AZD8076

dMAb AZD5396 and dMAb AZD8076 will be provided by the manufacturer to the University of Pennsylvania Investigational Drug Service (IDS).

Study product accounting will be performed continuously during the study. Details on study product volume, administration, and accountability are documented in the applicable study documents, i.e. CRF and on respective pharmacy forms.

It is the responsibility of the Investigator to ensure that a current record of investigational products disposition is maintained at the study site where investigational product is inventoried, dispensed and disposed. Records or logs must comply with applicable regulations and guidelines, and should include:

- Amount received and placed in storage area.
- Amount currently in storage area.
- Label ID number or batch number and use date or expiry date.
- Dates and initials of person responsible for each investigational product inventory entry/movement.
- Amount dispensed to each participant, including unique participant identifiers.
- Amount transferred to another area/site for dispensing or storage.
- Amount returned to Sponsor or designee.

- Amount destroyed at study site, if applicable.

At completion/termination of the study, all unused and partially used supplies must be returned to the Sponsor or designee. The investigator, pharmacist/drug administrator and monitor must verify that no drug supplies remain at the site at the time of study closeout. Appropriate records will be maintained in the investigator's site file.

6.1.2 *Formulation, Appearance, Packaging, and Labeling of dMAb AZD5396 and dMAb AZD8076*

dMAb AZD5396 and dMAb AZD8076 Drug Product is supplied in 2 R vials at a concentration of 10 mg/mL at a minimum recoverable volume of NLT 0.2 mL/vial. It is formulated in saline sodium citrate (SSC).

Appearance: Clear to slightly opalescent (\leq RS1; USP <855>), colorless solution (\leq Standard A; USP <631>), essentially free of visible particles.

Drug product labels are customized per local regulation, but the following information, at minimum, is included:

- Protocol identifier
- Investigational product name
- Dosage and formulation
- Lot number
- FDA required statement: "Caution: New Drug. Limited by Federal (or United States) law to investigational use."
- Expiration date
- Quantity in container

6.1.3 *Product Storage and Stability of dMAb AZD5396 and dMAb AZD8076*

The pharmacist at the University of Pennsylvania IDS will be responsible for assuring the quality of the investigational product is adequate for the duration of the trial. dMAb AZD5396 and dMAb AZD8076 will be shipped refrigerated. If the temperature logger is alarmed and displays a temperature deviation when the shipment is received, the Sponsor ([name]) and Inovio must be contacted immediately and IP quarantined until cleared for use by the manufacturer.

Investigational products must be stored in a secure area according to local regulations. All study products must be transferred from the shipping container to the appropriate storage conditions upon arrival. dMAb AZD5396 and dMAb AZD8076 must be stored refrigerated at 2 to 8°C.

Refrigerator/freezer temperature logs must be maintained at the clinical site and temperatures must be recorded and monitored regularly.

6.1.4 Handling, Preparation and Dispensing of dMAb AZD5396 and dMAb AZD8076

Investigational product is to be prepared by site staff who are trained and knowledgeable in mixing and dispensing investigational agents. For details, please review the Pharmacy Manual. Documentation of certification will be kept with the pharmacy documents. Study drug should be prepared in a BioSafety level 2 cabinet. Personnel will utilize proper aseptic technique per institutional guidelines.

It is the responsibility of the Investigator to ensure that dMAb AZD5396 and dMAb AZD8076 and CELLECTRA™ are only dispensed and administered to study participants. Authorized personnel at the official study site must be the only ones to dispense the product according to local regulations.

dMAb AZD5396 (pGX93321 and pGX93311) and dMAb AZD8076 (pGX93322 and pGX93315) drug products are formulated in a saline sodium citrate (SSC) buffer to a concentration of 10 mg/mL plasmid in 150 mM sodium chloride and 15 mM sodium citrate, which is supplied in 2 R glass vials and stored refrigerated at 5°C. Hylenex® Recombinant (human hyaluronidase injection) will be used for dose preparation at the clinical site. Hylenex® is approved in the US for intramuscular use to increase the dispersion and absorption of other injected drugs. In this Phase 1 clinical study, a 0.5 to 2 mg dose of dMAb AZD5396 and dMAb AZD8076 will be administered intramuscularly.

Dose preparation of each investigational product will occur within 4 hours prior to administration. For details about the preparation of the dose, consult the most current version of the Pharmacy Manual.

6.2 Hylenex® Recombinant

Hylenex® Recombinant is a purified preparation of the enzyme recombinant human hyaluronidase. It is produced by genetically engineered Chinese Hamster Ovary (CHO) cells containing a DNA plasmid encoding for a soluble fragment of human hyaluronidase (P20). Hyaluronidases are a family of enzymes that catalyze the degradation of hyaluronic acid. By catalyzing the hydrolysis of hyaluronic, a constituent of the extracellular matrix (ECM), hyaluronidase lowers the viscosity of hyaluronan, thereby increasing tissue permeability. Pre-treating the muscle with a hyaluronidase dose suitable for rats (0.56 U/g b.w.) prior to plasmid DNA injection increased transfection efficiency of injected plasmid by >200% ²². It is, therefore, used in conjunction with other drugs to speed their dispersion and delivery. dMAb AZD5396 and dMAb AZD8076 and Hylenex® Recombinant will be administered IM followed by EP to enhance plasmid dispersion in the delivery tissue ²³.

Hylenex® Recombinant will have both the original manufacturer's label on individual vials and the carton, and an additional label on the carton indicating the study number.

Refer to FDA approved package insert for additional information.

6.3 Investigational Device CELLECTRA™ 2000 with Side Port Needle

The investigational device used in the study is the CELLECTRA™ 2000 with Side Port Needle.

6.3.1 Acquisition and Accountability

The investigative site is responsible for maintaining investigational device and drug accountability logs. The drugs and device must have full traceability from the receipt of the products through the participant use, disposal or return of the products. The Site must document acknowledgement of receipt and notify Inovio upon receipt of the investigational products. This includes the content shipped and condition upon receipt.

For each participant administration, there must be a record of each product used for that participant, i.e., for the device, Pulse Generator serial number, applicator serial number, and array lot number. The CELLECTRA™ 2000 5P-IM Applicator is intended to be used multiple times on the same participant and then disposed after final use in accordance with accepted medical practice and any applicable local, state, and federal laws and regulations. Once the 5P-IM applicator is assigned to a participant, it may NOT be used on another participant. IM applicators used during device training conducted by Sponsor personnel or self-led refresher training must NOT be used on any participant. The used sterile disposable array attachment must be discarded after use in accordance with institutional policy regarding disposal of sharp needles/instruments.

6.3.2 Packaging and Labeling of Investigational Device

The CELLECTRA™ 2000 with Side Port device, and its components, and the Profusion Therapeutic Infusion needle (G47574) will be shipped directly from Inovio to the study site.

6.3.3 Use of CELLECTRA™ 2000 with Side port Electroporation Device

The treatment/electroporation procedure must be performed by qualified personnel. Any individual designated to perform the procedure should be permitted by the relevant local authorities to administer vaccinations or parenteral drugs to patients (e.g., MD, DO, RN). Non-licensed individuals (i.e., other than an MD, DO, or RN) may perform the treatment/electroporation procedure under both of the conditions below:

1. The non-licensed individual has been trained by the Manufacturer or its designee in intramuscular drug injection followed by EP. The non-licensed individual will perform the procedure under the direct supervision of the Principal Investigator or an approved Sub-Investigator who has already been trained by the Manufacturer or its designee.
2. The CV and any relevant qualifications of the individual have been reviewed and approved by the Sponsor ([name]) or its designee to perform the procedure.

All individuals designated to perform the EP procedure must satisfactorily complete device training from the manufacturer or its designee regardless of their qualifications. Any deviation from the above procedures must be approved by the sponsor and manufacturer or respective designee(s).

6.4 Return and Destruction of Investigational Products

Upon completion or termination of the study, all unused and/or partially used investigational product must be returned to the Sponsor ([name]) or its designee, if not authorized by the sponsor to be destroyed at the site.

All investigational products returned to the Sponsor ([name]) or its designee, must be accompanied by the appropriate documentation. Returned supplies should be in the original containers. It is the Investigator's responsibility to arrange for disposal for all empty containers, provided that procedures for proper disposal have been established according to applicable federal, state, local and institutional guidelines and procedures, and provided that appropriate records of disposal are kept. The return of unused investigational product(s) should be arranged by the responsible Study Monitor.

If investigational products are to be destroyed on site, it is the Investigator's responsibility to ensure that arrangements have been made for the disposal, written authorization has been granted by the Sponsor

([name]) or its designee, procedures for proper disposal have been established according to applicable regulation and guidelines and institutional procedures, and appropriate records of the disposal have been documented. The unused investigational products can only be destroyed after being inspected and reconciled by the responsible Sponsor ([name]), employee or designated person/team. Used investigational product must NOT be destroyed until accountability has been completed by the responsible Sponsor ([name]) employee or designated person/team.

6.5 Precautions with Investigational Medicinal Product

A dose of the study product known or suspected to have been taken (accidentally or intentionally) in excess of the dose mandated by the protocol, and any misuse or abuse of study products or any other product taken as a concomitant medication, whether or not associated with an adverse experience, must be reported to the Sponsor ([name]) within 24 hours. Any clinical sequelae in association with the overdose will be reported as an AE or SAE. Details of signs or symptoms, clinical management, and outcome should be reported, if available

7 STUDY PROCEDURES

Table 3. Schedule of Events Cohorts A-F

Tests and Observations	Screen Day -1 to -30	Day 0	Day 3 (cohorts B-F) $\pm 1d$	Day 7 $\pm 1d$	Day 10 (cohorts B-F) $\pm 1d$	W2 $\pm 2d$	W3 $\pm 2d$	W4 $\pm 2d$	W5 $\pm 2d$	W6 $\pm 4d$	W8 $\pm 2d$	W12 $\pm 7d$	W16 $\pm 7d$	W24 $\pm 7d$	W32 $+8w$	W42 $\pm 2w$	W52 $\pm 7d$	Additional PKs/ADAs, if needed	W72 $\pm 7d$	Additional PKs/ADAs, if needed ^k	Early Termination
Consent	X																				
Eligibility criteria	X																				
Demographics	X																				
Medical history	X	X	X	X	X	X	X	X	X	X	X	X	X	X		X		X		X	X
Conc. Meds ^a	X	X	X	X	X	X	X	X	X	X	X	X	X	X		X		X		X	X
Vital signs ^c	X	X	X	X	X	X	X	X	X	X	X	X	X	X		X		X		X	X
Physical Exam ^b	X	X	X	X	X	X	X	X	X	X	X	X	X	X		X		X		X	X
12-lead ECG	X	X	X	X	X	X	X	X	X	X	X	X	X	X		X		X		X	X
CBC w/diff	X	X	X	X	X	X	X	X	X	X	X	X	X	X		X		X		X	X
Chemistries ^d	X	X	X	X	X	X	X	X	X	X	X	X	X	X		X		X		X	X
HbA1c	X																				
Coagulation	X	X	X	X	X	X	X	X	X	X	X	X	X	X		X		X		X	X
Serologies ^e	X																				
CPK (with fractionation)	X	X	X	X	X	X	X	X	X	X	X	X	X	X		X		X		X	X
Pregnancy ^f	X	X	X																		
PK & ADA ^g		X	X	X	X	X	X	X	X	X	X	X	X	X		X		X		X	X
Urinalysis	X	X	X	X	X	X	X	X	X	X	X	X	X	X		X		X		X	X
NP swab for SARS-CoV-2	X																				

Tests and Observations	Screen Day -1 to -30	Day 0	Day 3 (cohorts B-F) $\pm 1d$	Day 7 $\pm 1d$	Day 10 (cohorts B-F) $\pm 1d$	W2 $\pm 2d$	W3 $\pm 2d$	W4 $\pm 2d$	W5 $\pm 2d$	W6 $\pm 4d$	W8 $\pm 2d$	W12 $\pm 7d$	W16 $\pm 7d$	W24 $\pm 7d$	W32 $+8w$	W42 $\pm 2w$	W52 $\pm 7d$	Additional PKs/ADAs, if needed	W72 $\pm 7d$	Additional PKs/ADAs, if needed ^k	Early Termination
Inoculation + EP		X	X																		
EP Data ^h		X	X																		
Memory aid ⁱ		X	X																		
VAS ^j		X	X																		
Injection Site Reactions		X	X	X	X																
AEs		X	X	X	X	X	X	X	X	X	X	X	X	X	X	X	X	X	X	X	

- a. Prior and concomitant, new medications will be recorded at all study visits (Day 0 through study discharge). Prior treatments, defined as administered up to 8 weeks prior to the time of informed consent, should be recorded in the CRF as prior medications.
- b. Full physical examination performed at screening and last visit or early termination only. Perform targeted examinations at other visits as determined by Investigator or per participant complaints. Record history of weight lifting or other significant physical activity.
- c. Vital signs will be performed pre and post inoculation at day 0, day 3, day 28, and day 31 visits; height and weight will be recorded at screening and final visit.
- d. Sodium (Na), potassium (K), chloride (Cl), bicarbonate (HCO3), glucose, BUN, Cr, ALT, AST
- e. HIV antibody or rapid test, HBsAg, HCV antibody.
- f. Serum pregnancy test at screening and urine pregnancy test thereafter
- g. Collect 3 tubes of whole blood (red top) to obtain ~10 mL serum at the indicated time points (this includes the PK sampling and ADA formation)
- h. Download EP data within 48 hours of dose and transfer to Sponsor or its designee
- i. Provide memory aid to study participants and review on next visit
- j. Obtain VAS score immediately after EP and at 5 and 10 minutes after injection. This is done after each injection, which are separated by 30 minutes.
- k. Up to 2 additional PK/ADA draws may occur up to 6 months after the participant's Week 72 target visit.

Table 4. Schedule of Events Cohort G

Tests and Observations	Screen Day -1 to -30	Day 0	Day 3 ±1d	Day 7 ±1d	Day 10 ±1d	W2 ±2d	W3 ±2d	Day 28 ±1d	Day 31 ±1d	W5 ±2d	W6 ±4d	W8 ±2d	W12 ±7d	W16 ±7d	W24 ±7d	W32 +8w	W42 ±2w	W52 ±7d	Additional PKs/ADAs, if needed	W72 ±7d	Additional PKs/ADAs, if needed ^k	Early Termination
Consent	X																					
Eligibility criteria	X																					
Demographics	X																					
Medical history	X	X	X	X	X	X	X	X	X	X	X	X	X	X	X	X	X	X	X		X	
Conc. Meds ^a	X	X	X	X	X	X	X	X	X	X	X	X	X	X	X	X	X	X	X		X	
Vital signs ^c	X	X	X	X	X	X	X	X	X	X	X	X	X	X	X	X	X	X	X		X	
Physical Exam ^b	X	X	X	X	X	X	X	X	X	X	X	X	X	X	X	X	X	X	X		X	
12-lead ECG	X	X	X	X	X	X	X	X	X	X	X	X	X	X	X	X	X	X	X		X	
CBC w/diff	X	X	X	X	X	X	X	X	X	X	X	X	X	X	X	X	X	X	X		X	
Chemistries ^d	X	X	X	X	X	X	X	X	X	X	X	X	X	X	X	X	X	X	X		X	
HbA1c	X																					
Coagulation	X	X	X	X	X	X	X	X	X	X	X	X	X	X	X	X	X	X	X		X	
Serologies ^e	X																					
CPK (with fractionation)	X	X	X	X	X	X	X	X	X	X	X	X	X	X	X	X	X	X	X		X	
Pregnancy ^f	X	X	X					X	X													
PK & ADA ^g		X	X	X	X	X	X	X	X	X	X	X	X	X	X	X	X	X	X	X	X	
Urinalysis	X	X	X	X	X	X	X	X	X	X	X	X	X	X	X	X	X	X	X		X	
NP swab for SARS-CoV-2	X																					
Inoculation + EP		X	X					X	X													
EP Data ^h		X	X					X	X													

Tests and Observations	Screen Day -1 to -30	Day 0	Day 3 ±1d	Day 7 ±1d	Day 10 ±1d	W2 ±2d	W3 ±2d	Day 28 ±1d	Day 31 ±1d	W5 ±2d	W6 ±4d	W8 ±2d	W12 ±7d	W16 ±7d	W24 ±7d	W32 +8w	W42 ±2w	W52 ±7d	Additional PKs/ADAs, if needed	W72 ±7d	Additional PKs/ADAs, if needed ^k	Early Termination
Memory aid ⁱ		X	X					X	X													
VAS ^j		X	X					X	X													
Injection Site Reactions		X	X	X	X			X	X	X	X											
AEs		X	X	X	X	X	X	X	X	X	X	X	X	X	X	X	X	X	X	X	X	

- a. Prior and concomitant, new medications will be recorded at all study visits (Day 0 through study discharge). Prior treatments, defined as administered up to 8 weeks prior to the time of informed consent, should be recorded in the CRF as prior medications.
- b. Full physical examination performed at screening and last visit or early termination only. Perform targeted examinations at other visits as determined by Investigator or per participant complaints. Record history of weight lifting or other significant physical activity.
- c. Vital signs will be performed pre and post inoculation at day 0, day 3, day 28, and day 31 visits; height and weight will be recorded at screening and final visit.
- d. Sodium (Na), potassium (K), chloride (Cl), bicarbonate (HCO3), glucose, BUN, Cr, ALT, AST
- e. HIV antibody or rapid test, HBsAg, HCV antibody.
- f. Serum pregnancy test at screening and urine pregnancy test thereafter
- g. Collect 3 tubes of whole blood (red top) to obtain ~10 mL serum at the indicated time points (this includes the PK sampling and ADA formation)
- h. Download EP data within 48 hours of dose and transfer to Sponsor or its designee
- i. Provide memory aid to study participants and review on next visit
- j. Obtain VAS score immediately after EP and at 5 and 10 minutes after injection. This is done after each injection, which are separated by 30 minutes.
- k. Up to 2 additional PK/ADA draws may occur up to 6 months after the participant's Week 72 target visit.

7.1 Screening Evaluations

The assessments performed during screening will determine the participant's eligibility for the study and also their ability to comply with protocol requirements by completing all screening assessments. Participants' post-menopausal status must meet requirements as specified in the inclusion criteria. The following screening evaluations will be performed within 30 days prior to dosing on Day 0. All screening assessment values must be reviewed prior to the first Study Treatment.

If a participant does not meet an inclusion or exclusion criterion due to a transient and non-clinically significant event at screening, relevant screening evaluations may be repeated within the same 30-day screening period. If the participant fails twice, they will be considered a screen failure.

The following evaluations will be performed during the screening period:

- Signed and dated informed consent.
- Collect demographics, including gender.
- Obtain and document complete medical history, surgical history (including all past procedures), present conditions, and concomitant illnesses.
- Full physical examination.
- Record current concomitant medications/treatments.
- Record vital signs including body weight and height, heart rate (HR), respiratory rate (RR), blood pressure (BP), oral temperature.
- Perform 12 lead ECG.
- Collect blood for PT(INR) and aPTT, HbA1C, CBC with differential, serum chemistry [sodium (Na), potassium (K), chloride (Cl), bicarbonate (HCO₃), glucose, blood urea nitrogen (BUN), creatinine (Cr)], AST, ALT, and CPK.
- Collect urine for urinalysis.
- Collect blood for serum pregnancy test.
- Collect serum for HIV, Hepatitis B surface antigen (HBsAg), and Hepatitis C serology.
- Review and confirm all inclusion/exclusion criteria.
- A nasal or nasopharyngeal (NP) swab for a COVID-19 test (note – a combination COVID-19+flu test will be done if required per current hospital policy).

7.2 Dosing and Follow-Up Evaluations

Once eligibility has been confirmed, the participant will be assigned to receive Investigational product. Visit dates and windows must be calculated from Day 0.

7.3 Day 0, Day 3, Day 28, and Day 31

The following evaluations will be performed on Day 0 (all cohorts), Day 3 (cohorts B-G), Day 28 (cohort G), and Day 31 (cohort G) only prior to Investigational product administration:

- Collect all present and/or new or ongoing adverse events (including history of new COVID 19 diagnosis).
- Document any present conditions and concomitant illnesses.
- Record current concomitant medications/treatments.
- Targeted physical examination (driven by symptoms).
- Record vital signs pre injection including heart rate (HR), respiratory rate (RR), blood pressure (BP), oral temperature.
- Collect urine for urinalysis and urine pregnancy test (if WOCBP).
- Collect blood for PT(INR) and aPTT, CBC with differential, serum chemistry, CPK.
- Collect serum for mAb AZD5396 and mAb AZD8076 level assessment and ADA evaluation.
- Provide Memory Aid.

Investigational product administration should occur after all the above pre-dose procedures have been completed.

Participants will receive two injections into the arm (deltoid)/leg (quadriceps) region at day 0 (all groups), and on day 3. Injections will be separated by ~30 minutes. Injections may be given in different arms or in an arm (deltoid) and a leg (quadriceps). If preferred or needed both doses can be done in the deltoid region or the lateral quadriceps, although the injections should be in different areas separated by at least 2 cm. The Day 3 injections may repeat an area already used on Day 0 as long as separated by at least 2 cm. For Cohort G, the Day 28 injections may be repeated in an area already used, and the Day 31 injections may repeat an area already used on Day 28 as long as separated by at least 2 cm.

If a participant has a DLT, as outlined in the protocol, the second dose of the product will not be given.

The following evaluations will be performed on Day 0 (all cohorts), Day 3 (cohorts B-G), Day 28 (cohort G), and Day 31 (cohort G) after Investigational product administration:

- Conduct targeted injection site reaction systemic and local assessments 30 min post each injection.
- Record vital signs post each injection including heart rate (HR), respiratory rate (RR), blood pressure (BP), oral temperature. Participants will be observed for 1 hour after the last injection.
- Perform 12 lead ECG after each injection.
- Collect any new adverse events after each injection.
- Complete VAS score immediately after EP and at 5 and 10 minutes post each injection.
- Download EP Data.
- Before the participant is discharged, we will wait until his or her vital signs are normal or have returned to their baseline before the injection.
- Normal vital sign ranges for the average healthy adult while resting are:
 - Blood pressure: systolic >90 and <140 mmHg, diastolic >60 and <100mmHg
 - Breathing: >9 and <20 breaths per minute

- Pulse: 60 to 100 beats per minute
- Temperature: Afebrile
- If the vitals do not return to baseline in 4 hours, the subjects will be maintained for observation in the hospital for continuous monitoring. This hospitalization will not be considered a SAE but a protocol procedure unless the event progresses and places the subject at risk.
- Participants will be reminded of the safety risk information included in the informed consent.

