8 STUDY INTERVENTION DISCONTINUATION AND PARTICIPANT DISCONTINUATION/WITHDRAWAL

8.1 Discontinuation of Study Intervention

Discontinuation from study intervention does not mean discontinuation from the study, and remaining study procedures should be completed as indicated by the study protocol. If a clinically significant finding is identified (including, but not limited to changes from baseline) after enrollment, the investigator or qualified designee will determine if any change in participant management is needed. Any new clinically relevant finding will be reported as an adverse event (AE).

The data to be collected at the time of study intervention discontinuation will include the following:

- Clinical laboratory evaluations (CBC, CMP, and any other necessary at the discretion of the PI).
- PK evaluation

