8.2 Participant Discontinuation/Withdrawal from the Study

Participants are free to withdraw from participation in the study at any time upon request. An investigator may discontinue or withdraw a participant from the study for the following reasons:

- Pregnancy
- If any clinical adverse event (AE), laboratory abnormality, or other medical condition or situation occurs such that continued participation in the study would not be in the best interest of the participant
- Disease progression which requires discontinuation of the study intervention
- If the participant meets an exclusion criterion (either newly developed or not previously recognized) that precludes further study participation

The reason for participant discontinuation or withdrawal from the study will be recorded on the Case Report Form (CRF). Subjects who sign the informed consent form and are scheduled for Day 0 but do not receive the study drug may be replaced. Subjects who sign the informed consent form and receive the study intervention, and subsequently withdraw, or are withdrawn or discontinued from the study, will be replaced at the discretion of the Investigator. Subjects in cohorts B, C, D, E, and F may be replaced if they do not receive both the Day 0 and the Day 3 doses. Subjects in cohort G may be replaced if they do not receive all four of the Day 0, 3, 28, and 31 doses. Subjects in these cohorts who

only receive Day 0 doses and want to continue in the study will be included in the A1 or A2 group for analysis.

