For women of child bearing potential (WOCBP), a serum pregnancy test will be obtained at screening and a urine pregnancy test will be performed prior to dosings. A negative result for urine β -HCG (test must have a sensitivity of at least 25 mIU/mL) must be available prior to each administration of Investigational product. If the β -HCG test is positive, indicating that the participant is pregnant prior to completing the specified dose regimen, then no further Investigational product will be administered. Every attempt should be made to follow pregnant participants for the remainder of the study and to determine the outcome of the pregnancy.

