10.10 Dose Limiting Toxicity Criteria

Dose limiting toxicities are defined below for the purposes of evaluating the safety of the administered doses of dMAb AZD5396 and dMAb AZD8076. The following Investigational product administration-and/or EP- related adverse events are defined as DLTs:

- Grade 3 or greater local injection site erythema, swelling, and/or induration recorded \geq 1 hour after Investigational product administration
- Pain or tenderness at the injection site that requires overnight hospitalization despite proper use of non-narcotic analgesics.

- Grade 3 or greater systemic symptoms assessed by the Principal Investigator as related to Investigational product administration.
- Grade 3 or greater clinically significant laboratory abnormalities assessed by the Principal Investigator as related to Investigational product administration.

The most severe grade for that particular event is to be documented on the CRFs for DLT.

DLT assessment is scheduled for the first 3 to 6 participants for specified cohorts at Day 14 (Week2). Study Investigators are required to conduct clinical assessment and review blood test results performed. The DSMB is responsible for reviewing available safety data for specified cohorts. Refer to Section [4.2](#) for additional information on DLTs and the dose escalation scheme.

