10.11 Stopping Rules (Criteria for Pausing Trial)

Refer to Study Design and Endpoints, for a description of “3+3” design and enrollment sequence of each cohort.

The stopping rules for this study are any of the following:

- If at any time during the study two thirds of participants in a single cohort experience a DLT after product administration
- If 2 or more participants across all enrolled cohorts experience the same grade ≥ 3 adverse event or grade ≥ 3 adverse event in the same organ class
- In the event of any unexpected Grade 4 toxicities
- Any SAE, potentially life-threatening AE or death
- Any reported anaphylaxis from dMAb AZD5396 and dMAb AZD8076 and Hylenex® delivered by EP.

The study will be halted for any report of anaphylaxis from dMAb AZD5396 and dMAb AZD8076 and Hylenex® delivered by EP. The study will be halted to enrollment and further dosing will be suspended until a full discussion has been conducted and then reviewed by the DSMB and study resumption is agreed upon.

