14.2 Safety and Quality Monitoring

14.2.1 Data Safety Monitoring Board

An independent DSMB will be established to protect participants through analysis of emerging data from the trial. The DSMB for this trial includes three medical experts not affiliated with the Sponsor ([name]) nor any participating trial center (including the Principal Investigator). This DSMB will conduct safety reviews prior to dose escalation and will also serve the role as the independent research monitor. In this role, the DSMB will review all unanticipated problems involving risks to participants or others and report all SUSARs to the Sponsor with an assessment of causality and relatedness and comment on whether they agree with the PI/site.

The DSMB will be responsible for reviewing all safety data, including DLTs, stopping rules and SAEs. Since this trial is an open-label trial, participants, the Principal Investigator and the Sponsor ([name]) are not blinded as to Investigational product allocation. The DSMB meeting frequency, scope, and other details will be described in a separate DSMB charter.

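### The mandatory DLT dosing rule in Section 7.3 withholds only the second dose, so it does not bar Cohort G's Day 28 doses, or its Day 31 doses after a Day 28 DLT

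*Protocol*

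**What the plan says.** Protocol Section 7.3 sets out procedures for Days 0, 3, 28 and 31 and names Cohort G for the last two. Its rule for a participant who has a DLT is: "If a participant has a DLT, as outlined in the protocol, the second dose of the product will not be given".

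Section 4.1 describes Cohort G as a four-dose regimen on those days. Table 2 gives 0.5 mg of each dMAb per dosing day and 2 mg of each in total. Section 9.5 counts 8 injections.

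Other provisions that bear on dosing after a toxicity:

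- **Section 4.2:** one DLT among the first three participants of a cohort goes to an ad hoc DSMB, which decides whether the study continues.
- **Section 8.1:** after a clinically significant finding, "the investigator or qualified designee will determine if any change in participant management is needed".
- **Section 8.2:** "An investigator may discontinue or withdraw a participant from the study for the following reasons"; adverse events are among the reasons listed.
- **Section 10.10:** defines DLTs, for example "Grade 3 or greater local injection site erythema, swelling, and/or induration recorded" at least 1 hour after administration, and schedules their assessment at Day 14.
- **Section 10.11:** trial-level pausing rules, one of which begins "If 2 or more participants across all enrolled cohorts experience the same grade" 3 or higher event, or one in the same organ class.
- **Section 14.2.1:** "The DSMB will be responsible for reviewing all safety data, including DLTs, stopping rules and SAEs".

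The pregnancy rule in Section 9.4.5 is worded differently. After a positive test, "then no further Investigational product will be administered".

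**The concern.** The rule in Section 7.3 reads as wording for a two-dose regimen that was not updated when Cohort G was added. The heading, the assessment lists and the injection-site text of that section all mention Days 28 and 31, and the replacement rule in Section 8.2 refers to all four doses. The DLT sentence still stops at the second.

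Cohort G is the only cohort re-exposed about four weeks after its first doses, and Section 4.1 lets the Day 28 injections reuse a Day 0 or Day 3 area with no separation. A participant with a Grade 3 local reaction could therefore be injected again at the same site without breaching any stated dosing rule. At stake is the safety of a healthy volunteer. No estimate, endpoint or escalation decision changes.

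**Working it through.** The protocol states no figure to reproduce. The check counts which Cohort G doses the rule bars, by time of DLT, and then looks for any other rule that bars the rest.

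**Inputs**

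- Dosing days 0, 3, 28 and 31 (Section 4.1).
- Two injections per dosing day, one per dMAb: 4 × 2 = 8 injections (Section 9.5).
- 0.5 mg of each dMAb per dosing day: 4 × 0.5 = 2 mg of each (Table 2).
- In a four-dose regimen on these days, the second dose is Day 3.

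**Literal effect of the Section 7.3 rule in Cohort G**

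| DLT occurs | Dosing days left | Barred | Not barred | Injections not barred | mg of each dMAb not barred | Share of 2 mg |
|---|---|---|---|---|---|---|
| After Day 0, before Day 3 | 3, 28, 31 | 3 | 28, 31 | 2 × 2 = 4 | 2 × 0.5 = 1 | 50% |
| After Day 3, before Day 28 | 28, 31 | none | 28, 31 | 2 × 2 = 4 | 2 × 0.5 = 1 | 50% |
| After Day 28, before Day 31 | 31 | none | 31 | 1 × 2 = 2 | 1 × 0.5 = 0.5 | 25% |

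In Cohorts B to F the only later dose is Day 3, so the same sentence bars everything that remains.

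**How long the gap stays open.** Day 3 has a window of ±1 day (Days 2 to 4) and Day 28 a window of ±1 day (Days 27 to 29) (Table 4). The interval is nominally 28 − 3 = 25 days, at least 27 − 4 = 23 and at most 29 − 2 = 27. Four scheduled visits fall inside it: Day 7, Day 10, Week 2 and Week 3. Safety blood samples are taken at each, and related Grade 3 laboratory abnormalities that are clinically significant count as DLTs. Any DLT first found at one of these visits comes after the second dose.

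**Other readings of the term.** If it means the second injection on the same day, later dosing days remain open. If it means the second dose of each pair, Day 31 is barred after a Day 28 DLT, but Day 28 is still open after a Day 0 or Day 3 DLT. No available reading closes the gap.

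**Whether another rule closes it**

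- Section 4.2: the board decides on the study and on whether a dose level is tolerated. It does not decide on the affected participant's doses.
- Sections 8.1 and 8.2: left to the investigator.
- Section 10.10: definition and a Day 14 assessment, with no dosing consequence.
- Section 10.11: pauses the trial for any SAE, a potentially life-threatening event, an unexpected Grade 4 toxicity, anaphylaxis, repeated Grade 3 or higher events across participants, or DLTs in two thirds of a cohort. With five participants the last needs 4, since 3/5 = 60% falls short of 66.7%. A pause does not fix what happens to the individual on resumption.
- Section 10.13.2: expedited FDA reporting of any DLT, with no dosing consequence.
- Section 14.2.1: DSMB review, with no dosing consequence.

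The case that meets no mandatory pause and no mandatory bar is therefore a single non-serious, related Grade 3 DLT with no earlier Grade 3 or higher event in that organ class. Injection-site erythema above 10 cm (Grade 3 in Table 5), recorded at least 1 hour after dosing, is an example.

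**The case against.** The strongest reply is that no careful investigator would redose such a participant and that the protocol offers several checks. Adverse events are collected before every dose. Section 8.1 requires a management decision after a clinically significant finding. A DLT in any of Cohort G's first three participants goes to an independent board, and every DLT is reported to the FDA in an expedited manner. So the event would not go unseen, and the case with neither a pause nor the ad hoc board review narrows to the fourth or fifth participant.

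The Day 0 scenario is also somewhat strained. It requires Day 3 to be withheld for toxicity and dosing then to restart on Day 28, and Sections 8.2 and 11.3.6 place participants who receive only Day 0 doses with A1 or A2 for analysis. Finally, the second-of-each-pair reading would remove the Day 28 to Day 31 gap.

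Most of this stands as mitigation. It limits how likely harm is and supports treating the matter as a wording defect. It does not supply the missing rule. Board review and FDA reporting decide nothing about that participant's next dose, the A1/A2 provision is an analysis assignment, and the pair reading is stated nowhere and leaves Day 28 open. The Day 3 to Day 28 interval, which is the longest and contains four safety visits, is untouched by any of these arguments.

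**Conclusion.** The concern holds. As written, the protocol's only mandatory participant-level DLT rule fails for Cohort G, the cohort with the most dosing days. It leaves 4, 4 or 2 of the 8 injections without a mandatory bar, depending on whether the DLT follows Day 0, Day 3 or Day 28.

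This rests on reading the second dose as Day 3, which is the natural meaning in a regimen the protocol calls four-dose. The Day 28 gap after a Day 0 or Day 3 DLT does not depend on that reading. The practical reach is small: five evaluable participants, partial safeguards, and an evident intention that a DLT should end a participant's dosing. It should be fixed because the text falls short of that intention in healthy volunteers and the correction is trivial.

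**What to change.** Replace the DLT sentence in Section 7.3 with:

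> If a participant has a DLT, that participant receives no further investigational product; all remaining planned doses are withheld.

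This brings it into line with the pregnancy rule in Section 9.4.5 and works for every cohort. As an optional clarification, Section 10.10 could say that DLT review in Cohort G also covers the Day 28 and Day 31 doses, using the existing Week 5 and Week 6 visits.

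The cost is one sentence, with no added visit or sample. Section 8.1 already keeps a participant who stops dosing in follow-up, and Section 8.2 already provides: "Subjects in cohort G may be replaced if they do not receive all four of the Day 0, 3, 28, and 31 doses". The only possible expense is a replacement participant.
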